## 6.4 Followup for Adverse Events

The Investigator will follow up moderate and severe adverse events until it is resolved/stable. The study sponsor will be notified when the issue has been resolved.

## 7. INTERVENTION DISCONTINUATION

A participant in the trial has the right to discontinue treatment at any point within the trial for any reason. If the subject does choose to discontinue, a reason for discontinuation will be recorded and every effort will be made to collect end of study information. Every effort will be made by the Investigator to address any issues before discontinuing the subject such as answering questions on use.

Due to the exploratory nature of this intervention, a possible pause on enrollment and discontinuation of active subjects may occur if the sponsor discovers a serious issue with the use of the device. This could include events such as a subject hospitalization resulting from the direct use of the device. The study will not continue to enroll additional subjects until the root cause has been identified and corrected.

A study contract will be issued from the sponsor company to the investigator. Inability of the study investigator to meet expectations such as enrollment, documentation, or communication to the sponsor, may result in the study sponsor discontinuation of the study. The study sponsor has the ability to discontinue the entire study at any point and even between both phases for any reason necessary. The intervention is not a lifesaving device therefore it will not pose a risk to subjects.

## 8. STATISTICAL CONSIDERATIONS

### 8.1 General Design Issues

The primary objective of this study is to compare the comfort, tolerability of generator settings and demonstrate the effectiveness of the surface Elidah device.

In the first study of the Elidah device, the protocol was designed to remain as simple as possible for both the subject and the investigator while still obtaining the information necessary for the study sponsor to further development of the device. This study was broken into two distinct phases to first test comfort between generator settings. The second phase of the study will then evaluate efficacy.

### 8.2 Sample Size

The sample size was determined by the small pilot nature of this study and similar clinical studies. Study subjects are being recruited through advertisements, flyer or internal database. The number of recruited subjects will continue until the number of enrolled participants is satisfied. As this is an acute study, and enrollment is on day of study, we do not expect any dropouts prior to the study however an estimated 20% may not feel contractions.

|                            | Phase I   |
|----------------------------|-----------|
| Subjects to be Enrolled    | 8 (12max) |
| Projected Withdraw Rate    | 20%       |
| Total Number of Completers | 5-6       |

Subjects will have a unique screen number, according to chronological screening entry, and a corresponding subject number after informed consent is received.

### 8.3 Interim Analyses and Stopping Rules

The study is small and acute, and so was purposely designed to avoid any interim analyses from occurring. In the event of a SAE with direct correlation to the device, the study will be temporarily halted until the safety issue can be addressed. Only 1 SAE will trigger this halting in enrollment. Due to the small enrollment size, the number of unanticipated problems or adverse events will not spur an interim analysis or early end to the study.

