## 6.2 Adverse Events and Serious Adverse Events

An **adverse event (AE)** is generally defined as any unfavorable and unintended symptom or sign which either occurs during the study, having been absent at baseline, or if present at baseline, appears to worsen. Adverse events are to be recorded regardless of their relationship to the study intervention.

A **serious adverse event (SAE)** is generally defined as any untoward medical occurrence that results in death, is life threatening, requires insubject hospitalization or prolongation of existing hospitalization, results in persistent or significant disability/incapacity, or is a congenital anomaly. Solicited adverse events will be collected at the office visits.

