## 6.3 Reporting Procedures

Adverse events will be reported from the clinical site to the sponsor within 24 hours.

The sponsor will use the following 0 to 4 scale to grade adverse events (AE): 0 = none or event is not clinically significant, 1 = mild AE that does not require treatment, 2 = moderate AE that does require treatment, but resolves completely and 3 = severe AE, e.g., results in temporary inability to conduct one or more everyday activities and requires ongoing medical attention, and 4 = life threatening or results in permanent inability to conduct one or more everyday activities.

In the event of an adverse event to a subject in the proposed study, the site investigator will discuss the available medical treatment options with the subject. If an AE occurs, the Sponsor will assist the subject in obtaining appropriate medical attention if unable to be performed by the Investigator. If treatment or hospitalization is required as a result of participation in this study, the subject and their insurance carrier are responsible for the cost of medical care. The subject will not lose any of their legal rights and they do not release the Sponsor, investigators, the study staff, or study site from liability for mistakes or intentional misconduct by participating in the study.

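### Below a device-correlated SAE, no event, count or time point calls for a cumulative safety look, and Section 8.3 says adverse event numbers will not prompt one

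*Combined protocol and SAP*

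**What the plan says.** Section 8.3 plans no interim analyses and gives the small size and acute nature of the study as the reason. It sets one mandatory trigger: after a single SAE directly correlated with the device, "the study will be temporarily halted until the safety issue can be addressed". It closes by saying that "the number of unanticipated problems or adverse events will not spur an interim analysis or early end to the study".

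Other sections add oversight:

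- Section 6: each adverse event is assessed for seriousness and for a causal link to the device. Device-associated events are followed until they resolve or stabilize.
- Section 6.3: "Adverse events will be reported from the clinical site to the sponsor within 24 hours". The sponsor grades events from 0 to 4. Grade 2 is an event that needs treatment and resolves completely; Grade 3 is severe.
- Section 7: the sponsor may pause for a serious device issue, and "The study sponsor has the ability to discontinue the entire study at any point and even between both phases for any reason necessary".
- Section 9.3: the sponsor's clinical director oversees safety data and monitors conduct halfway through enrollment of both phases. A DSMB will review adverse events; no timing is given.
- Section 10.4: the IRB, the FDA and other bodies may discontinue the study.

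Section 5b opens Phase II, in men, once the ultrasound protocol has been carried out successfully in women. Only the screening and the electrode differ, and the male electrode is a prototype.

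**The concern.** The last sentence of 8.3 is a stated rule, not a silence. It stands under a heading that covers stopping rules as well as interim analyses, and it makes no exception for grade, device-relatedness or repetition.

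Suppose two of the first few subjects need treatment for a device-related reaction. Each report reaches the sponsor within a day and is graded. Nothing in the plan says that the two together call for a review before the next session, and 8.3 can be read as saying that they do not. The same rules carry into Phase II, where a different electrode is used at a new anatomical site. The condition for opening that phase is technical success of the imaging, not a look at Phase I safety.

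At stake is the exposure of the remaining subjects to a device problem that falls short of an SAE.

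**Working it through.** **Step 1: which events lead to what.**

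| Event | Required action in the documents |
|---|---|
| Device-correlated SAE | Halt (8.3) |
| Device-related Grade 3, not an SAE | Report, grade, assess cause, follow up; no cumulative look |
| Repeated device-related Grade 2 | Same |
| Unanticipated problem, not an SAE | No cumulative look; 8.3 says the number does not prompt one |
| Move from Phase I to Phase II | A stop is allowed (7); no safety look is required |

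Some Grade 3 events could meet the SAE criterion "results in persistent or significant disability/incapacity" in 6.2. The clearest gap is therefore Grade 2 events and unanticipated problems.

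**Step 2: inputs.** The goal is N = 8, with a minimum of 5 and a maximum of 12 (3.3). Section 8.3 states no operating characteristic, so there is no figure of the plan's own to reproduce. The documents give no adverse event rate. Per-subject rates p of device-related Grade 2 or higher events are assumed at 2%, 5%, 10% and 20%, with 20% as a high value for sensitivity only. Subjects are taken as independent and treated one at a time.

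**Step 3: two or more events.** P(X ≥ 2) = 1 − (1−p)^N − N·p·(1−p)^(N−1).

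- N = 8, p = 0.10: 1 − 0.4305 − 0.3826 = 0.187.
- N = 12, p = 0.10: 1 − 0.2824 − 0.3766 = 0.341.

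**Step 4: subjects still to be treated after the second event.** The unconditional mean is the sum over k = 2 to N of (N−k)·(k−1)·p²·(1−p)^(k−2). Multiplying by p gives the mean number of events avoided if every review stopped the study, which is the upper limit of benefit for a two-event trigger.

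| p | N | P(X ≥ 2) | Mean remaining | Mean events avoided |
|---|---|---|---|---|
| 2% | 8 | 0.010 | 0.02 | 0.0004 |
| 2% | 12 | 0.023 | 0.08 | 0.0016 |
| 5% | 8 | 0.057 | 0.12 | 0.006 |
| 5% | 12 | 0.118 | 0.44 | 0.02 |
| 10% | 8 | 0.187 | 0.44 | 0.04 |
| 10% | 12 | 0.341 | 1.41 | 0.14 |
| 20% | 8 | 0.497 | 1.36 | 0.27 |
| 20% | 12 | 0.725 | 3.72 | 0.74 |

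At the minimum of N = 5, P(X ≥ 2) is 0.023 at 5% and 0.081 at 10%.

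**Step 5: how often a fuller trigger fires.** Suppose a review follows one Grade 3 or higher event, two Grade 2 or higher events, or any unanticipated problem, all device-related. Let q be the Grade 3 or higher part of p, and u the rate of unanticipated problems, taken as independent. With a = (1−p)(1−u) and b = (p−q)(1−u), P(fires) = 1 − a^N − N·b·a^(N−1).

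For p = 0.02, q = 0.005 and u = 0.005, a = 0.9751 and b = 0.014925:

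- N = 8: 1 − 0.8173 − 0.1001 = 0.083.
- N = 12: 1 − 0.7389 − 0.1357 = 0.125.

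**Step 6: benefit at that same 2%.** For the fuller trigger, mean subjects remaining is the sum over k = 1 to N−1 of 1 − a^k − k·b·a^(k−1), which is 0.285 (N = 8) and 0.680 (N = 12). Multiplied by 0.02, this gives about 0.006 and 0.014 Grade 2 or higher events avoided, even if every review stopped the study. At a low event rate the trigger rarely fires and does very little.

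**The case against.** The strongest reply is that a numeric trigger in a single-sitting pilot of 5 to 12 subjects is an option that no requirement in the documents demands. The plan gives its reason for having no interim analyses. Intensity is controlled by the subject and starts from zero, the device switches off after 20 minutes, and Section 6.1 cites an FDA classification of similar devices as non-significant risk. The same section lists the expected effects, such as skin redness and tingling, as known side effects and not as unanticipated problems. This helps to explain why 8.3 does not count adverse events. All of it stands, and it keeps the weight low. It does not cover truly unanticipated problems or repeated device-related events that need treatment.

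The halfway monitoring in 9.3 is a timed check and deserves credit. It is a sponsor check of conduct and reporting, however; it is not a cumulative safety review and does not gate Phase II.

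A reader might infer that 8.3 forbids a safety pause or leaves subjects unprotected. The documents do not support that: the sentence does not bar a discretionary pause, and the sponsor, IRB and FDA can all stop the study.

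A reader might also infer a real conflict with Section 7, where "a possible pause on enrollment and discontinuation of active subjects may occur if the sponsor discovers a serious issue with the use of the device", with "a subject hospitalization resulting from the direct use of the device" as the example. Such a hospitalization is an SAE under 6.2, so 8.3 already makes the halt mandatory. Section 7 covers a wider class of issues, for which permissive wording is natural. Its restart condition is the stricter one: "The study will not continue to enroll additional subjects until the root cause has been identified and corrected". Both sections can be followed together, so this is a difference in wording and no safeguard is missing.

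**Conclusion.** The point holds in a narrow form. Section 8.3 rules out the number of adverse events or unanticipated problems as a reason for an interim analysis or early end, and nothing elsewhere supplies an event, count or time point below a device-correlated SAE that calls for a cumulative look. That includes the step to the male prototype electrode.

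The size is modest. On assumed rates, a two-event trigger would avoid about 0.04 (N = 8) to 0.14 (N = 12) events at 10% and almost none at 2%. It approaches one event only at 20% with 12 subjects (0.74). Those figures are upper limits, because they assume that every review ends the study. The expected benefit is small unless the true rate is high, which is the situation a trigger is meant to catch. This is a minor improvement that is worth making because it is cheap. No sample size or analysis changes.

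**What to change.** 1. Limit the last sentence of 8.3 to efficacy interim analyses.
2. Have the DSMB named in 9.3 promptly review cumulative device-related events after one device-related Grade 3 or higher event, two device-related Grade 2 or higher events, or any device-related unanticipated problem. This starts a review, not an automatic halt; the board advises on pausing.
3. Have the DSMB look at the Phase I adverse event listing before Phase II opens.

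Making Section 7 mandatory for a device-related SAE, to match 8.3, is optional tidying.

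The cost is protocol wording only, since the board and the grading scale already exist. The downside is a possible short delay to sessions. Under the 2% assumptions above, the trigger would fire in 8.3% (N = 8) to 12.5% (N = 12) of studies, and each firing costs one review of a listing of at most 12 subjects.

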### 8.4 Outcomes

As discussed in Section 1, Study Outcomes, will be analyzed until the study has been closed to enrollment. Some outcome measures simply relate to the comfortability and usability of the device which is best described anecdotally and will contribute to future recommendations for better compliance. The objective data can be statistically analyzed to observe differences in treatment group and considerations including severity of UI, age, and demographic information.

#### 8.4.1 Primary Outcome

- Movement of pelvic floor with electrical stimulation

#### 8.4.2 Secondary Outcomes

- Comparison of movement with electrical stimulation, Kegels, and both
- Indication of which muscle groups are activating

## **9. DATA COLLECTION AND QUALITY ASSURANCE**

### **Information and/or Specimen Management**

Each device may be reused for different subject, with a wipe down with alcohol in between uses. Each subject will use a new electrode(s).

The label for the Elidah electrode will bear the following information:

- Name and address of the contact
- Investigational Trial Application statement
- Study number
- Storage instructions
- Contents
- Lot number

At the conclusion of the study, all unused Elidah electrodes and generators will be counted, reconciled with dispensing records, documented, and returned to Elidah or their designee. The Clinical Monitor will assure that a final report of electrode accountability is prepared and placed in both the Investigator's Study File and the Sponsor's Study File.

After completing the trial, all unused Elidah electrodes and returned generators will be shipped to Elidah at:

Elidah, Inc, [name]

### **9.1 Data Collection Forms**

The CRF data, with screening, will be recorded on paper forms or through spreadsheet, cloud folders.

Any electronic data shared between the study sponsor and the study site will only include subject numbers and will not include any identifying subject data. Any electronic forms will be stored on an external drive lockable or password-protected cloud system. At the conclusion of the study the study sponsor will retain all subject information and forms under lock and key for a minimum of seven years after last subject participation (based on HIPAA privacy). The study sponsor may decide to transfer all paper data to electronic data which will follow the same regulations.

### **9.2 Data Management**

At the conclusion of the study and close-out monitoring visit the study site will transfer all data to the study sponsor. All management of the data entry will be the responsibility of the study sponsor in addition to auditing of the data. An individual at the study sponsor not directly in contact with study data will audit the transferring of data captured on paper to date entered into a digital database. A statistical analysis plan will be created which will also include procedures for auditing of the data.

### **9.3 Data and Safety Monitoring Plan**

The Clinical director of Sponsor will oversee safety data collection as reported from subjects. Demonstration of use will be at the first visit, Instructions for Use will be sent home with the subjects, and a phone number for both the site and study sponsor will be provided to the subjects for any questions or reporting of adverse events. After the first week of use at home, a call will be made to each subject to ensure the subjects are using the device correctly and do not have any issues. Currently, electrical stimulation, such as TENS units, are sold over the counter and are used at home,

so we believe this level of monitoring is considered appropriate and the overall likelihood of harm is low.

To ensure that the rights and well-being of human subjects are protected; the reported trial data are accurate and complete, and verifiable from source documents; and the conduct of the trial is in compliance with the currently approved protocol, with GCP, and with the applicable regulatory requirements, an experienced Clinical Director will monitor the conduct of the study halfway through enrollment of both Phases of the study. In the plan, the clinical director will throughout the trial period:

- Act as the main line of communication between the Sponsor and the investigator
- Verify that facility, laboratories, equipment and staff are adequate to safely and properly conduct the trial
- Verify that the investigator
  - is adequately informed about the trial, as well as investigators' staff
  - has adequate qualifications and resources
  - follows the approved protocol and any amendments
  - receives all documents and supplies necessary
  - is enrolling only eligible subjects
  - provides all the required reports, notifications, applications and submissions
- Verify, for the investigational product:
  - That the storage times and conditions are acceptable, and that supplies are sufficient throughout the trial
  - That the SU1 product is supplied only to subjects who are eligible to receive it and with the correct quantity
  - That the subjects are provided with necessary instruction on proper use, handling, storage, and return of the product
  - That the receipt, use, and return of the product are controlled, documented, and complies with regulations
- Verify that written informed consent was obtained before each subject's participation in the trial
- Report subject recruitment rate
- Verify that source documents and trial records are accurate, complete, and up to date
- Determine whether all adverse events are appropriately reported within time periods required
- Communicate deviations from the protocol and make appropriate actions.

In addition, a Data Safety and Monitoring Board will be established for this project and will review the study design, IRB protocol, adverse events and findings of the study.

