### **3.5 Study Enrollment Procedures**

Subjects will be recruited through normal standard of care visits, office visits, and current subjects. A flyer will be posted in the waiting room.

1. The study director will go through the "Screening" checklist, which will include initial screening inclusion and exclusion criteria.
2. The Screening checklist will be kept in a Screening Log binder at the site and each screened potential subject will be recorded on the initial screening log chronologically.
3. If the subject is a candidate, the study administrator or physician will describe the study, walk the subject through the consent and obtain consent.
4. Day 1 of the study may be on the same day as initial screening if time allows, or up to 21 days later.
5. If subject is still a candidate, then the subject will be entered into the enrollment log and assigned the next subject/enrollment number. A copy of the initial screening will be put in the Case Report Sheet and the subject number recorded.

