### 3.8 Concomitant Medications

Not Applicable - as this is a single-sitting acute study.

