### 5.2 Electrode

The electrode is configured as a single unit contoured to fit against the perineal tissues with a hole in the center through which bodily fluids can pass. The skin-contacting surfaces are conductive gel regions located at the four corners with a hole in the center of the pad. Snaps and a cable is used to connect to the generator which may be worn at the waist. Benchtop testing has been completed to ensure that the resulting current passing through the Elidah electrode is similar to currently marketed 2" square patch electrodes.

Packaging: Foil pouch

Reusability: The electrode is designed to be used for one hour or less. This is an acute study and it is not expected for electrodes to be reused. A new electrode should be used for each subject.

Storage: Unused electrodes should be stored in sealable storage bag so that the gels does not dry out.

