### **10.2 Informed Consent Forms**

An informed consent document that includes both information about the study and the consent form will be prepared and given to the subject. The document will be prepared in a language understandable to the subject and appropriately describes the responsibilities of the study staff and subject in partaking in the study and any potential risks. An individual from the Study site will review every page with the study subject. The subject is free to ask any questions and may take as much time to read through the document as possible.

If the subject agrees to the informed consent, they will sign two copies of the informed consent and the staff who gave informed consent will also sign both copies. One signed copy will remain in the subject folder, the second copy will be given to the study subject.

No minors will be enrolled in the trial, and those that are unable to consent for themselves will not be eligible to participate by a legal guardian. Individuals who do not speak English will be excluded from enrolling in this study in addition to those who cannot read. Due to the independent and at-home nature of the trial these populations would not be able to perform the daily activities required and no extra provisions will be made for them.

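### The only scheduled safety contact after the session is tied to home use that this single-sitting study does not provide, so later reactions are captured only if the subject reports them

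*Combined protocol and SAP*

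**What the plan says.** On the design, sections 3.6, 3.7 and 3.8 each give the same answer: "Not Applicable - as this is a single-sitting acute study". Section 3.5 schedules nothing after the session itself: "Day 1 of the study may be on the same day as initial screening if time allows, or up to 21 days later". Section 4.4 places all stimulation within one ultrasound session. Section 5.2 says of the electrode: "This is an acute study and it is not expected for electrodes to be reused". Section 9 (Information and/or Specimen Management) lets generators pass between subjects: "Each device may be reused for different subject, with a wipe down with alcohol in between uses".

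On safety, section 9.3 has use demonstrated at the first visit and the instructions for use sent home, and then states: "After the first week of use at home, a call will be made to each subject". It also provides a passive route: "a phone number for both the site and study sponsor will be provided to the subjects for any questions or reporting of adverse events". Section 6.2 states: "Solicited adverse events will be collected at the office visits". Section 6 has events recorded, whether observed or volunteered, at visits and at any other contact. Section 6.1 asks subjects to contact staff if redness or sensitivity recurs.

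On eligibility, section 10.2 excludes people who do not speak English or cannot read, and gives this reason: "Due to the independent and at-home nature of the trial these populations would not be able to perform the daily activities required". The exclusion list in 3.2 has no such criterion.

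**The concern.** Section 6 makes adverse events the main basis for judging the safety of the device. The call in 9.3 is the only point at which anyone would contact a subject after she leaves, and its timing is counted from an event that does not take place. A site following the text literally would never make the call. A site that made it anyway would have to choose its own interval, and these could differ between subjects.

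Later reactions are plausible from the plan's own account. Section 6.1 expects that redness or sensitivity may be present after the electrode is removed. Section 4.4 takes intensity to the maximum comfortable level, then repeats the test with a possible increase because the skin may become numb. It is a fair inference, though not a statement in the protocol, that numb skin could hide irritation until after the session.

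At stake is what a low or zero event count would mean. For events during the session it would rest on observation and solicited collection. For events after it, the count would rest on volunteered reports alone, and a reader of 9.3 would wrongly believe that every subject had been called.

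**Working it through.** No arithmetic applies: the plan gives no adverse-event rate and plans no bound on one. The check is to set the sections side by side.

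1. **Does any procedure provide home use?** Sections 3.6 to 3.8 call the study a single sitting. Section 4.4 contains the whole stimulation sequence. Section 5.2 expects no reuse of electrodes, and section 9 lets generators be shared. Section 5.1 mentions home use, but as a feature of the product. Section 9.3 speaks of a week at home and 10.2 of daily activities, yet neither is matched by a procedure, visit or dispensing step in section 4. The answer is no.

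2. **Is any office visit placed after the session?** Under 3.5, screening and Day 1 are either the same day or up to 21 days apart, with screening first. There are thus one or two visits, and neither follows the session. Solicited collection under 6.2 therefore ends when the session visit ends.

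3. **Which safety routes remain after the visit?**
   - Active and scheduled: one is written (the call in 9.3), and none is operative, because its starting point does not occur.
   - Passive: three provisions remain in force, none of them dependent on home use. These are the phone numbers (9.3), recording of events at any contact (6), and the instruction to contact staff about recurring redness or sensitivity (6.1).

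4. **Do the other safeguards ask subjects about later events?** Under 9.3 the sponsor's clinical director oversees data as subjects report them, and a monitoring board reviews adverse events. Section 6.3 sets 24 hours for the site to report to the sponsor. Section 6.4 follows moderate and severe events to resolution. Each acts on an event already known, and none elicits one.

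5. **Is a collection window defined after the session?** None is stated.

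6. **Do 10.2 and 3.2 agree?** No. The criterion in 10.2 is absent from 3.2, and the reason given for it fails at step 1.

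**The case against.** The strongest case against is that this is leftover wording in a low-risk study, and that post-visit capture is planned. Much of that stands. A reader might infer from the broken trigger that reactions after the visit are not captured at all. The documents do not support this: the phone-number provision sits in 9.3 itself, and sections 6 and 6.1 add two more routes. Nor does safety monitoring as a whole rest on home use, given the clinical director's oversight, the monitoring board, 24-hour reporting and follow-up of known events.

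It is also true that several risks in 6.1 (shock, pain from poor gel contact, redness on removal) would tend to arise while the subject is still on site. A zero count would remain informative about those. The documents give no incidence for delayed reactions, so the number that might be missed cannot be estimated. Whether one supervised session with a device described as non-significant risk needs active follow-up is partly a matter of judgement.

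That judgement has, however, already been made in the plan. Section 9.3 includes the call among the measures it then describes as an appropriate level of monitoring. The objection does not explain how the call would be made.

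On eligibility, a reader might infer that screening would let through people whom 10.2 excludes. The screening checklist is a separate document and is not available here. Under 3.5, consent also precedes entry in the enrollment log, so the exclusion could still be applied at that step. What stands is only that the reason does not fit this study and the criterion is unlisted.

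**Conclusion.** The point holds in a limited form. The one active, scheduled safety contact after the session cannot be triggered as written, solicited collection stops at the visit, and later reactions depend on self-report. This applies to every subject in Phase I (8 planned, up to 12). It carries into Phase II in men, which section 5b describes as identical apart from screening and the electrode. The primary displacement endpoint is unaffected.

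The conclusion assumes that the single-sitting description governs and that the home-use text does not belong to this study. Sections 3.6 to 3.8, 4.4, 5.2 and 9 (Information and/or Specimen Management) all point that way. If the sponsor does intend home use, the contradiction remains and those sections would need to change instead.

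The mismatch between 10.2 and 3.2 is a separate and smaller matter with the same apparent source. The change should be made, but the fault is not fatal to the study.

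**What to change.** In 9.3, remove the home-use text and time the planned call from the imaging session, at an interval the sponsor and investigator set. Add a solicited adverse-event question to the call, and amend 6.2 so that solicited collection includes it. If no call is wanted, state in 9.3 that safety after the session rests on spontaneous reports only, and describe any zero count in those terms when results are reported.

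Separately, in 10.2 either drop the language and literacy exclusion or give a reason that applies to a single supervised session, and list the criterion in 3.2.

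The cost is a wording amendment and 8 to 12 short calls in Phase I. The protocol already intends those calls, and only their starting point and content change. Phase II would add one call per man; the protocol gives no number for that phase.
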